#### 5.9 Subject Withdrawal/Discontinuation Criteria

Subjects may withdraw consent at any time for any reason or be withdrawn from the trial at the discretion of the investigator should any untoward effect occur. In addition, a subject may be withdrawn by the investigator or principal investigator if enrollment into the trial is inappropriate, the trial plan is violated, or for administrative and/or other safety reasons. Specific details regarding discontinuation or withdrawal are provided in Section 7.1.4 – Other Procedures.

A subject must be discontinued from the trial for any of the following reasons:

- The subject or legal representative (such as a parent or legal guardian) withdraws consent.
- Confirmed radiographic disease progression
- Unacceptable adverse experiences as described in Section 5.2.1.2
- Intercurrent illness that prevents further administration of treatment

- Investigator's decision to withdraw the subject
- The subject has a confirmed positive serum pregnancy test
- Noncompliance with trial treatment or procedure requirements
- The subject is lost to follow-up
- Administrative reasons

The End of Treatment and Follow-up visit procedures are listed in Section 6 (Protocol Flow Chart) and Section 7.1.5 (Visit Requirements). For those subjects discontinue treatment early, each subject will be followed for 30 days for adverse event monitoring (serious adverse events will be collected for 90 days after the end of treatment as described in Section 7.2.3.1). Subjects who discontinue for reasons other than progressive disease will have post-treatment follow-up for disease status until disease progression, initiating a non-study cancer treatment, withdrawing consent or becoming lost to follow-up. After documented disease progression each subject will be followed for overall survival until death, withdrawal of consent, or the end of the study, whichever occurs first.

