13. Patients with residual disease (SD, PR, or PD) on post-treatment imaging will undergo salvage surgical resection (at the discretion of the surgeon) if their disease is felt curable with salvage surgery. Additionally, patients with a CR and clinical suspicion for viable residual disease will be offered salvage surgery. Following pathology analysis, salvage surgical tissue will be sent for correlative studies. Detailed instructions for tissue collection, processing, and shipment are included in the procedures manual.

14. PET imaging at baseline and treatment end is not required for the study, but is allowed for use to determine complete response rate when tumor response on standard imaging cannot confirm CR based on RECIST 1.1. Please see sections 7.1.2.6.2 and 7.1.2.6.3 for details.

15. Screening labs completed within 7 days (168 hours) of treatment initiation (day -7) will not need to be repeated.

16. Once a subject experiences confirmed disease progression or starts a new anti-cancer therapy, the subject moves into the Survival Follow-Up Phase. These subjects will be followed every 6 months to assess for survival status until death, withdrawal of consent, or the end of the study, whichever occurs first.

17. If a subject discontinues pembrolizumab, return visit timing is left to treating physician discretion until day 150 although it is highly recommended that the subject return for Day 78, 120, and 150 so research specimens and QOL can be collected.

18. Minimum interval between pembrolizumab doses is 14 days.

19. Vital signs and weight do not need to occur on the same day as the visit but need to be completed within the window and prior to the next treatment.

20. Once a subject transitions to follow-up all documented AEs will be followed until resolution or to a new baseline as determined by the treating investigator. Only new AEs that could be considered an ECI or irAR will be documented and followed while in follow-up.

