#### 7.1.5.5 Follow-up Visits

Follow-up visits for subjects who complete study treatment are outlined in the Trial Flow Chart – section 6.

Subjects who discontinue trial treatment for a reason other than disease progression will move into the Follow-Up Phase. Every effort should be made to collect information regarding disease status until the start of new anti-cancer therapy, disease progression, death, or end of study. Information regarding post-study anti-cancer treatment will be collected if new treatment is initiated.

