#### 7.1.5.6 Survival Follow-up

Once a subject experiences confirmed disease progression or starts a new anti-cancer therapy, the subject moves into the Survival Follow-Up Phase. These subjects will be followed every 6 months to assess for survival status until death, withdrawal of consent, or the end of the study, whichever occurs first.

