#### 8.4 Analysis Endpoints

#### 8.4.1 **Efficacy Endpoints**

Radiographic Complete response (rCR) rate: proportion of subjects in the analysis population who have a complete response on RECIST 1.1 imaging at treatment end.

PET NPV rate: proportion of subjects in the analysis population who are considered to have NPV based on Hopkins Criteria scoring at treatment end.

Pathologic complete response (pCR) rate: proportion of subjects in the analysis population who have stable disease (SD) or partial response (PR) on RECIST 1.1 imaging at treatment end, who undergo salvage surgical resection and have a complete response determined on histologic evaluation.

Overall Complete Response (CR) rate: this is a composite proportion of subjects in the analysis population with a rCR, PET NPV, and pCR. This is the primary measure of efficacy for the study.

Overall Response Rate (ORR): proportion of subjects in the analysis population who have complete response (CR) or partial response (PR) based on RECIST 1.1 imaging at treatment end.

Progression-Free Survival (PFS): time from Day -7 treatment administration to the first documented disease progression or death.

Overall Survival (OS): time from Day -7 treatment administration to death due to any cause.

Locoregional Control (LRC): time from day -7 treatment to date of local or regional relapse within the primary radiation treatment field (relapse in the head or neck region, excluding CNS recurrence).

Rate of Distant Metastases (DM): proportion of subjects in the analysis population who develop distant recurrence, as defined by recurrence outside of the primary radiation treatment field (head and neck region).

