#### 8.4.3 Statistical Methods

#### 8.4.3.1 Statistical Methods for Efficacy Analyses

The efficacy endpoints, analysis population, and statistical methods (including missing data handling) that will be employed for the efficacy analyses are presented in Table 7.

The primary endpoint is the total CR rate (composite outcome of rCR, PET NPV, and pCR) on all subjects. We have designed the study to test the hypothesis that the CR rate will be greater than 40.2% assuming a rate of 60.4%. To test this, we will use a one sample, one-sided asymptotic equality test with the null hypothesis that the total CR rate will be 40.2%. This test will result in a p-value greater than 0.05 if fewer than 21 patients respond to treatment. Secondary endpoints will include rCR, pCR, PET NPV, PFS, OS, LRC, and DM rates. For the secondary endpoints, we will only estimate confidence intervals to understand the possible range of values rather than doing formal hypothesis testing. Survival curves for PFS and OS will be constructed using the Kaplan-Meier method and 1 and 2-year survival estimates will be calculated.

Endpoint Statistical Method		Analysis Population	Missing data approach			
rCR Rate	Exact binomial method: Clopper-Pearson 95% confidence interval	FAS	Subjects with missing data are considered non-responders			
pCR Rate	Exact binomial method: Clopper-Pearson 95% confidence interval	FAS 	Subjects with missing data are considered non-responders			
CR Rate	One sample, one-sided asymptotic binomial test	FAS	Subjects with missing data are considered non-responders			
Objective Response Rate (CR + PR)	Exact binomial method: Clopper-Pearson 95% confidence interval	FAS	Subjects with missing data are considered non-responders			
PFS (RECIST 1.1) by independent radiology review	Summary statistics using Kaplan-Meier method	ASaT	Censored at last assessment date			
OS	Summary statistics using Kaplan-Meier method	ASaT	Censored at last assessment date			
LRC rate	Exact binomial method: Clopper-Pearson 95% confidence interval	FAS	Subjects with missing data are considered as disease not under control			
DM rate Exact binomial method: Clopper-Pearson 95% confidence interval		FAS	Subjects with missing data are considered as disease not under control			

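### Table 7 reports LRC and DM as undated proportions that count missing status as failure, so neither row gives the 1- and 2-year rates the objectives ask for.

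*Combined protocol and SAP*

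**What the plan says.** - **Table 7, LRC and DM rows (Section 8.4.3.1).** Each is a single proportion in the FAS with a Clopper-Pearson 95% interval. Neither row names a time point. The missing-data entry for both is "Subjects with missing data are considered as disease not under control".
- **Table 7, PFS and OS rows.** These use Kaplan-Meier in ASaT, with missing data "Censored at last assessment date". The text of Section 8.4.3.1 plans 1- and 2-year estimates for these two endpoints only.
- **Endpoint definitions (Section 8.4.1).** The first is a time to event: "Locoregional Control (LRC): time from day -7 treatment to date of local or regional relapse". DM is the "proportion of subjects in the analysis population who develop distant recurrence, as defined by recurrence outside of the primary radiation treatment field", with no date attached.
- **Objectives and design.** Section 3.2 asks for LRC and DM rates at 1 and 2 years. Section 2.1 describes DM as a cumulative incidence.
- **Follow-up.** Section 7.1.5.6 states: "Once a subject experiences confirmed disease progression or starts a new anti-cancer therapy, the subject moves into the Survival Follow-Up Phase". Footnote 16 under Section 6.3 adds: "These subjects will be followed every 6 months to assess for survival status until death, withdrawal of consent, or the end of the study". Section 5.9 agrees for progression: "After documented disease progression each subject will be followed for overall survival until death, withdrawal of consent, or the end of the study". For patients who stop treatment for another reason, Section 7.1.5.5 asks sites to "collect information regarding disease status until the start of new anti-cancer therapy, disease progression, death, or end of study".
- **Imaging.** Only neck imaging is required (Section 7.1.2.6.1; footnote 12 under Section 6.3). Section 7.1.2.6.2 asks that imaging done for clinical signs of progression be reported, but sets no schedule after a first failure.

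**The concern.** The two rows do not estimate what the objectives name. An undated proportion depends on how long patients happen to be followed, and it gives neither a 1-year nor a 2-year figure.

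The missing-data rule adds a second problem. It suits a response endpoint read once at treatment end, but here it applies to years of follow-up. The FAS requires treatment-end imaging, so missing LRC or DM status arises mainly after about day 150, through loss to follow-up or new therapy. A patient lost while disease-free then becomes both a locoregional failure and a metastasis. Relative to recorded status, the rule can only raise DM and lower LRC, by an amount set by follow-up and not by disease.

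The stake is moderate. Section 4.2.3.1 plans to compare these secondary endpoints with historical data. It allows favourable and statistically sound results to inform whether the combination goes forward.

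**Working it through.** **No figure to reproduce.** The documents give no expected rate, precision or dropout for LRC or DM. The denominators 57, 34 (HPV+) and 23 (HPV-) come from Section 2.1. All event and loss counts below are assumptions.

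**1. Shift per patient.** One patient scored as failing moves a rate by at most 1/N:
- 1/57 = 1.75 points
- 1/34 = 2.9 points
- 1/23 = 4.3 points

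The shift is zero if that patient truly had the event.

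**2. Narrow reading: a documented failure of one type is not missing data for the other.** Let m be patients lost, or starting new therapy, without progression. Reported DM = (recorded DM + m)/N, so the overstatement from the rule is 0 to m/N. With 6 recorded DM events and N = 57:

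| m | Reported DM | 95% CI | Overstatement, points |
|---|---|---|---|
| 0 | 6/57 = 10.5% | 4.0 to 21.5 | 0 |
| 3 | 9/57 = 15.8% | 7.5 to 27.9 | 0 to 5.3 |
| 6 | 12/57 = 21.1% | 11.4 to 33.9 | 0 to 10.5 |

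The maximum overstatement does not depend on the event count. With 9 recorded events, reported DM is 15.8%, 21.1% and 26.3% for the same m. LRC mirrors this: with 6 recorded locoregional failures it falls from 51/57 = 89.5% (m = 0) to 45/57 = 78.9% (m = 6).

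**3. Broad reading: status on the other endpoint is missing once follow-up is survival-only.** Let a be locoregional-first and b distant-first failures. Then reported DM = (a + b + m)/N and reported LRC = 1 - (a + b + m)/N, so DM equals 1 minus LRC exactly. With a = b = 6 and m = 0, DM is 12/57 = 21.1% (11.4 to 33.9) and LRC is 45/57 = 78.9% (66.1 to 88.6). If event-free patients have no undetected metastases, true any-time DM lies between 6/57 = 10.5% (no locoregional-first patient later metastasises) and 12/57 = 21.1% (all six do). The overstatement is then 0 to 10.5 points. In general, with m = 0 it is 0 to a/57: up to 5.3 points for a = 3 and 15.8 for a = 9.

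**4. The missing time point.** Assume 2-year first-event probabilities of 10% locoregional, 10% distant and 5% lost, with constant hazards and no deaths modelled. The probability of any first event by year T is F(T) = 1 - 0.75^(T/2), giving 13.4%, 25.0% and 51.3% at 1, 2 and 5 years. The distant share is 10/25 and the lost share 5/25.

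| Year | First-event DM, 0.4F | Table 7 DM, narrow, 0.6F |
|---|---|---|
| 1 | 5.4% | 8.0% |
| 2 | 10.0% | 15.0% |
| 5 | 20.5% | 30.8% |

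The same row can thus report very different rates depending on when the data are cut.

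**The case against.** A reader might infer that the plan collapses DM into 1 minus LRC, because follow-up turns survival-only at progression. The documents do not support that as a stated rule. Nothing says that moving to survival follow-up makes status missing, and under the Section 8.4.1 definition a patient with a documented locoregional relapse and no recorded metastasis reads more naturally as a non-event. The collapse is one possible consequence of an undefined term. Under the narrow reading with nobody lost, the effect is zero.

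Other points on that side also have weight:
- **Provisions that limit missing status.** Section 7.1.2.6.2 falls back on clinical evaluation when insurance refuses a CT and suggests PET/CT at 1 year. Section 7.1.4.1 allows partial withdrawal with continued follow-up. Every follow-up visit includes a directed examination.
- **Method.** With complete status at a fixed time, the simple proportion equals cumulative incidence with death competing. The defect is the absent date and the missing-data rule, not the binomial method as such.
- **Impact.** The endpoints are unpowered, reported by interval only, and the rule is conservative. By itself it cannot create false superiority.
- **Opposite bias.** With only neck imaging required, undetected metastases would lower reported DM.
- **Other text.** Section 8.4.7.4 mentions proportional hazards models for subgroups, and Section 8.2 points to a separate SAP.

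These points limit the size and importance of the problem. They do not remove it. The subgroup models supply no overall 1- or 2-year estimate, and Table 7 states its rule outright, against Sections 2.1, 3.2 and 8.4.1.

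**Conclusion.** The concern holds as a mismatch between Table 7 and the protocol's own objectives, together with a missing-data rule that turns a loss without metastasis into a DM event. The firm figure is the maximum shift per imputed patient: 1.75 points at 57, 2.9 at 34 and 4.3 at 23. Everything beyond that rests on assumed counts. Three to six losses would overstate DM by at most 5.3 to 10.5 points on the narrow reading. The broad reading would add more, but the text does not adopt it.

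The primary CR analysis is untouched, and the rule works against the regimen. The change should be made because it is cheap and because these rates are meant for historical comparison. The conduct of the trial does not depend on it. Nor do the documents support going further and redefining DM as site of first failure. That would change the Section 8.4.1 endpoint, omit later metastases, and could look favourable beside historical any-time rates.

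**What to change.** In Table 7, replace the LRC and DM rows with 1- and 2-year cumulative incidence of locoregional failure and of distant metastasis, measured from day -7 (Aalen-Johansen, 95% CI).
- Treat death without the event as a competing event.
- Censor event-free patients at the last disease assessment relevant to that endpoint, and say what counts as a distant assessment when only neck imaging is required.
- Report LRC as 1 minus the locoregional-failure incidence.
- Keep the Section 8.4.1 definition of DM, and state that a documented failure of one type is not by itself missing data for the other.
- Keep missing-equals-failure as a worst-case sensitivity analysis.
- If wanted, add a site-of-first-failure analysis, labelled as supplementary.

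The cost is wording and standard software, with no new data. Because Table 7 sits in the protocol, Section 8.2 may require an amendment if these count as key secondary hypotheses.

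Two limitations should be written down. Censoring is assumed non-informative, including at new therapy without progression. Metastases after a locoregional first failure may be under-recorded, because only survival status is planned from then on.

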8.4.3.2 Table 7: Statistical Methods for Key Efficacy Endpoints

Patient Reported Outcomes (PRO)	Linear mixed model to compare with historical controls over time.	ASaT	Missing data will not be included	
1 – only those who undergo salvage surgery				

#### 8.4.4 Statistical Methods for Safety Analyses

Safety and tolerability will be assessed by clinical review of all relevant parameters including adverse events (AEs), laboratory tests, and vital signs. Count and percentage of AE will be provided. Clopper-Pearson 95% confidence interval for the proportion of AE of clinical interest will be estimated using exact method based on binomial distribution. AE rates will be compared, using a Fisher's exact test to compare the proportions. This will also be compared to historical data from patients treated on a similar clinical trial using high-dose bolus cisplatin in combination with radiation which was recently performed at the primary study site (Sanford Cancer Center, Sioux Falls and Sanford Roger Maris Cancer Center, Fargo).

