# 3.0 OBJECTIVE(S) & HYPOTHESIS (ES)

#### 3.1 **Primary Objective(s) & Hypothesis(es)**

1. **Objective:** To determine the safety and tolerability of pembrolizumab given in combination with cisplatin-based chemoradiotherapy (CRT) in subjects with treatment naive Stage III-IVB squamous cell carcinoma of the head and neck (SCCHN).

**Hypothesis**: Pembrolizumab can be safely added to cisplatin-based CRT and will be well tolerated in patients with Stage III-IVB SCCHN.

2. **Objective:** To evaluate the efficacy of pembrolizumab given in combination with definitive CRT by complete response rate at treatment end in patients with HPV+ SCCHN and HPV-SCCHN.

**Hypothesis**: The addition of pembrolizumab to standard CRT will provide a 75% or greater CR rate in patients with Stage III-IVB HPV- SCCHN and a 90% or greater CR rate in patients with Stage III-IVB HPV+ SCCHN.

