A fixed dose regimen will simplify the dosing regimen to be more convenient for physicians and to reduce potential for dosing errors. A fixed dosing scheme will also reduce complexity in the logistical chain at treatment facilities and reduce wastage.

Rationale for weekly cisplatin based chemoradiotherapy:

Cisplatin based chemoradiotherapy (CRT) remains the mainstay for definitive treatment for LA-SCCHN. Various dosing regimens exist; however high-dose bolus cisplatin given at a dose of 100 mg/m2 on days 1, 22, and 43 of radiation remains the standard of care based on phase III data [12, 13]. Other dosing regimens include weekly cisplatin, daily cisplatin, and various combination regimens [14]. NCCN guidelines outline several options using cisplatin including high-dose bolus cisplatin, cisplatin in combination with 5-fluorouracil, cisplatin in combination with paclitaxel, and weekly cisplatin given at a dose of 40 mg/m2 [15]. While high-dose bolus cisplatin is the preferred choice due to randomized clinical trial data, weekly cisplatin is increasingly becoming a popular choice in clinical practice [16].

Several reasons for weekly cisplatin gaining favor exist. First of all, toxicity with high-dose bolus cisplatin is very high. Nephrotoxicity, neurotoxicity, ototoxicity, and the high emetic risk with this regimen have led to investigations into other regimens. Furthermore, many patients are unable to tolerate all three bolus doses, leading to potentially decreased efficacy [17].

While high-dose bolus cisplatin has never formally been compared head to head with weekly cisplatin in a phase III randomized trial, there have been smaller, single-institution comparisons both retrospectively and prospectively [16, 18, 19, 20]. In these studies, weekly cisplatin has been clearly better tolerated and efficacy does not seem to be impaired. Therefore, current NCCN guidelines indicate that weekly cisplatin given at a dose of 40 mg/m2 during radiation is an option, albeit with a category 2B recommendation (Category 2B: Based on a lower level of evidence, there is an NCCN consensus that intervention is appropriate).

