#### 4.2.3 **Rationale for Endpoints**

#### 4.2.3.1 Safety and Efficacy Endpoints

Safety and efficacy are the primary endpoints for this study. Safety is an important endpoint for a study like this for a number of factors. First of all, the inflammatory events surrounding chemoradiation, while potentially allowing for improved immune clearance with pembrolizumab, may end up causing more toxicity. The PD-1: PD-L1 pathway is important in normal, healthy individuals in protecting from autoimmunity during inflammatory events. As CRT will induce an inflammatory event in the head and neck region, one can surmise that PD-L1 and PD-1 upregulation may be a normal response meant to protect from autoimmune events. Evaluation of safety during and following this period is paramount to understanding the role of PD-1 inhibitors combined with CRT. While a certain level of toxicity is expected with this combination, special attention will be paid to immune-related toxicities and exacerbation of known CRT related toxicities. If this combination is not felt to be safe, it would not be recommended to move forth with further evaluation.

Efficacy is the co-primary endpoint for the study. This endpoint is important to estimate the clinical benefit of this combination. If there is little to no added benefit with this combination, it would not be recommended to move forth with additional studies utilizing this combination. If the treatment is efficacious, it would be reasonable to consider phase III testing of this combination, comparing it to high-dose bolus cisplatin.

Complete response rate was chosen as the primary efficacy measure. While progression-free survival may be a reasonable alternative to this efficacy measure, complete response rate was chosen based on several factors. First, this was the efficacy measure in preclinical studies that suggested this combination was efficacious. Second, this outcome can be compared to the Intergroup Trial [13], which evaluated high-dose bolus cisplatin in a phase III setting. In this study, imaging and clinical response were used to determine response rate. The complete response rate in those treated with high-dose bolus cisplatin was 40.2% among 87 analyzable patients. While the imaging and response criteria from that study does not directly match what

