## 4.2.3.3 Exploratory Research

As previously mentioned, we have data from a randomized phase 2 trial in this setting, in this same patient population [35]. The study utilized high-dose bolus cisplatin 100 mg/m2 on days 1, 22, and 43 with or without the agent dichloroacetate (DCA). From this study, we have historically banked specimens from 40-50 patients undergoing primary CRT. These specimens include tumor RNA/DNA (freshly isolated), tumor blocks of primary and metastatic nodal specimens, peripheral immune cells isolated to remain live and functional. Quality of life analyses, response data, and survival data were also prospectively collected and can be correlated to outcomes. These data will be used as a control to ascertain changes seen with the addition of PD-1 inhibition as proposed in this study. This data, combined with the correlative studies performed during this study, can provide valuable insight into biomarkers for treatment response, targets for future therapy, and other potential factors that may impact efficacy and safety, as we enter the field of chemoimmunoradiotherapy.

While this is still developing in this field, several of the key areas of exploratory research in this setting include: circulating immune cell analysis, tumor infiltrate immune cell analysis, the HPV specific immune response [11], and tumor genomic alterations [36]. We have the capability to collect specimens and evaluate each of these factors during and following CRT. As previously mentioned, we have experience with these procedures from a prior study in a similar population. Furthermore, our cancer biology COBRE grant funding and core facilities will help fund and assist in this testing.

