#### 5.4 **Randomization or Treatment Allocation**

The study is non-randomized. There is only one treatment arm. All subjects will receive the study treatment.

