#### 7.2 Assessing and Recording Adverse Events

An adverse event is defined as any untoward medical occurrence in a patient that received a pharmaceutical product during the course of the study, whether or not they are considered related to the product. This includes changes in laboratory parameters. Any medical condition that is present before the subject starts study medication and does not deteriorate should not be reported as an AE. However, if it deteriorates at any time during the study it should be recorded as an AE.

Changes resulting from normal growth and development that do not vary significantly in frequency or severity from expected levels are not to be considered adverse events. Example of this may include, but are not limited to, menopause occurring at a physiologically appropriate time.

Adverse events may occur during the course of the use of Merck product in clinical trials or within the follow-up period specified by the protocol, or prescribed in clinical practice, from overdose (whether accidental or intentional), from abuse and from withdrawal.

Progression of the cancer under study is not considered an adverse event unless it is considered to be drug related by the investigator.

All acute adverse events will be recorded from the time the subject receives the first dose of treatment through 30 days following cessation of treatment. The reporting timeframe for adverse events meeting any serious criteria is described in section 7.2.3.1.

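### The historical adverse-event comparison changes the cisplatin schedule and adds pembrolizumab together, with no common observation window, so an equal or lower rate does not support the Section 3.1 safety hypothesis

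*Combined protocol and SAP*

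**What the plan says.** Section 4.2.3.1 states: "Safety and efficacy are the primary endpoints for this study". The safety hypothesis in Section 3.1 concerns an addition: "Pembrolizumab can be safely added to cisplatin-based CRT and will be well tolerated in patients with Stage III-IVB SCCHN". Section 5.4 confirms that "There is only one treatment arm", so there is no concurrent comparator.

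Section 8.4.2 bases the primary safety analysis on CTCAE toxicities and grades in this trial's own patients. Section 8.4.4 gives counts, percentages and Clopper-Pearson intervals for AEs of clinical interest, and then says: "AE rates will be compared, using a Fisher's exact test to compare the proportions". No groups are named. The next sentence brings in the external controls: "This will also be compared to historical data from patients treated on a similar clinical trial using high-dose bolus cisplatin in combination with radiation". The Section 8.1 summary repeats Fisher's test under key safety analyses, again without groups. No common window, exposure adjustment, margin or safety criterion is stated.

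On the two cisplatin schedules, Section 4.2.2 says: "In these studies, weekly cisplatin has been clearly better tolerated and efficacy does not seem to be impaired". It later repeats that the weekly schedule is the less toxic of the two.

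On collection, Section 7.2 says: "All acute adverse events will be recorded from the time the subject receives the first dose of treatment through 30 days following cessation of treatment".

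**The concern.** The Section 3.1 hypothesis asks what pembrolizumab adds to cisplatin-based CRT. The only comparator named for AEs had a different cisplatin schedule, one that the plan itself describes as more toxic. A difference in schedule can therefore hide toxicity that pembrolizumab adds. Separately, the proportion of patients with at least one AE rises with observation time, and nothing in Section 8.4.4 equalises that time. If the historical patients were observed for less time, this trial would show an apparent excess even with no drug effect. The two biases act in opposite directions and the documents do not allow them to be netted. At stake is the reading of a null or favourable Fisher result as support for safety, or of an unfavourable one as harm from pembrolizumab.

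**Working it through.** The plan states no power, margin or threshold for AEs, so there is no figure to reproduce. Fisher probabilities below are exact enumerations at two-sided 5% (the level is assumed).

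**Sample sizes.** This trial: 57 (Section 1.0). Historical: 40-50 patients with banked specimens (Section 4.2.3.3) and 27 + 12 = 39 evaluable for CR (Section 4.2.3.5). The number with AE data is not given, so 39 and 50 are both used.

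**1. Cisplatin schedule.** Let W be the AE proportion on weekly-cisplatin CRT alone, D what pembrolizumab adds, and B the proportion on bolus CRT. The trial observes W + D, so the comparison estimates

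(W + D) − B = D − (B − W).

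The plan's own account is that B exceeds W. An observed difference of zero or less is then compatible with any D up to B − W. This needs no numerical assumption. The documents give neither W nor B, so the following only illustrates it, with W = 40% and D = 20 points (trial 60%):

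| Assumed B | Excess harm flagged, 57 v 39 | 57 v 50 |
|---|---|---|
| 40% (no schedule effect) | 44% | 49% |
| 50% | 13% | 15% |
| 60% | 2% | 2% |
| 70% | 0.1% | 0.1% |

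At B = 70% the trial regimen looks significantly safer in 14% (n = 39) or 16% (n = 50) of trials, despite the 20-point addition.

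**2. Observation window.** Pembrolizumab runs from Day -7 to Day 141 (Section 5.2, Table 2), and Day -7 is seven days before Day 1 (Section 2.1). Elapsed time to the end of AE collection is 7 + 140 + 30 = 177 days, or 178 calendar days counting both ends. This is a maximum, because patients who stop early are followed for 30 days from stopping.

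The historical window is not in the documents. Assumption: Day 1 to Day 80 (CRT ending about Day 50, plus 30), which is 80 calendar days. This trial then has 178 − 80 = 98 further days: the loading week and Days 81-171.

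Assume a 30% control proportion and no drug or schedule effect. The daily hazard inside the 80 days is h = −ln(0.70)/80 = 0.00446. Let the hazard in the other 98 days, almost all after CRT, be r × h. The trial proportion is

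p = 1 − exp[−h(80 + 98r)].

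| r | p | Fisher rejects, 57 v 50 | 57 v 39 |
|---|---|---|---|
| 0 (no window effect) | 30.0% | 4% | 4% |
| 0.10 | 33.0% | 5% | 5% |
| 0.25 | 37.2% | 10% | 9% |
| 0.50 | 43.7% | 28% | 23% |
| 1.00 | 54.8% | 70% | 64% |

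The result depends strongly on the assumed control window. With 120 days, the control exposure becomes 80 + 40r and p = 1 − 0.70^[(80 + 98r)/(80 + 40r)]. For r = 0.10, 0.25, 0.50 and 1.00, p is 31.7%, 33.9%, 36.9% and 41.1%, and rejection (57 v 50) is about 4%, 6%, 9% and 19%. With 150 days, p at r = 1 is 1 − 0.70^(178/150) = 34.5% and rejection is about 6%. With equal windows the inflation disappears.

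**3. Precision.** The 95% half-width for a difference is 1.96 × √[p(1 − p)(1/57 + 1/n)]. This is 17 points at p = 30%, n = 50, and 20 points at p = 50%, n = 39. With no margin set, a non-significant result would not show comparability even without bias.

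**The case against.** A reader might infer that the co-primary safety conclusion rests on a Fisher test against bolus-cisplatin controls and is therefore invalid. The documents do not support that. Section 8.4.2 makes the primary safety analysis descriptive. No success criterion or stopping rule depends on the historical comparison, and early safety review is left to DSMB judgement (Section 8.4.7). In Section 8.4.4 the historical sentence follows the Fisher sentence and is worded as an addition, so tying the test to those controls is an inference. It is a reasonable one in a single-arm trial, since no internal AE groups are named, but what the text shows directly is that the groups are undefined.

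A reader might also infer that the longer window here will produce a false excess, perhaps in most trials. That is not established either. The historical AE window is not given. Section 4.2.3.5 shows that historical patients were assessed about three months after radiation; this does not fix their AE window, but it makes 80 days uncertain. The 70% figure needs a hazard outside the CRT window equal to the hazard within it with no drug effect, which sits poorly with the acute CRT toxicity the plan describes. At r = 0.10 there is almost no inflation.

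Section 4.2.2 also gives a purpose that the comparison does fit: whether the whole regimen is as safe as bolus-cisplatin CRT. And a window ending 30 days after radiation would drop real pembrolizumab events from the tested comparison. That cost stands, which is why those events need separate reporting.

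None of this answers the schedule problem: for the Section 3.1 hypothesis, the comparator differs in two respects at once.

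**Conclusion.** The concern holds for a supporting comparison, not for the primary safety analysis as defined. From the documents alone, an AE rate equal to or below that of bolus-cisplatin CRT is not evidence that pembrolizumab is safely added, and the groups for Fisher's test are not specified.

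The window bias is conditional. If the historical window was shorter than up to about 177 days, crude proportions here are biased upward. Its size can be given only as a range: rejection in about 5%, 10%, 28% and 70% of trials for r of 10%, 25%, 50% and 100%, against 4% with no window effect. That range rests on 57 v 50 patients, an 80-day control window, a 30% control proportion and no drug effect. A longer control window shrinks it. The schedule bias runs the other way and cannot be sized from the documents, so the net direction is unknown.

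**What to change.** In Section 8.4.4, and in the matching row of the Section 8.1 summary:

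- Name the groups that Fisher's test compares.
- Limit the tested historical comparison to a window common to both studies: CRT start to 30 days after the last radiation fraction, or the historical window if shorter. Make this conditional on historical AE onset dates being available; if they are not, keep the comparison descriptive with no test.
- Report loading-dose, adjuvant-phase and full-period AEs separately, with exact intervals.
- If the historical study is the randomized trial described in Section 4.2.3.3, where cisplatin was given with or without dichloroacetate, also show the comparison with controls who did not receive it.
- State that the comparison is regimen against regimen, the question raised at the end of Section 4.2.2, and is not evidence for the Section 3.1 hypothesis. Judge that hypothesis on this trial's own immune-related and Grade ≥3 rates with exact intervals. Section 8.4.4 already plans such intervals for AEs of clinical interest.

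The cost is SAP wording and a date filter on this trial's data, plus a check of what the historical dataset holds. Some pembrolizumab-phase events leave the tested comparison but are still reported. Leaving out dichloroacetate-treated controls makes the control group smaller and that comparison less precise.
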